8.3.1.6. Follow-up of Adverse Events

All AEs experienced by a subject, irrespective of the suspected causality, will be monitored until the event has resolved, until any abnormal laboratory values have returned to baseline or stabilized at a level acceptable to the Investigator and Medical Monitor, until there is a satisfactory explanation for the changes observed or until the subject is lost to follow-up.

8.3.1.7. *Pregnancy*

The Sponsor has a responsibility to monitor the outcome of all pregnancies reported during the clinical study.

Pregnancy alone is not regarded as an AE unless there is a suspicion that the study drug may have interfered with the effectiveness of a contraceptive medication. Elective abortions without complications should not be regarded as AEs, unless they were therapeutic abortions (see below). Hospitalization for normal delivery of a healthy new-born should not be considered a SAE.

Each pregnancy must be reported by the Investigator to the Sponsor within 2 days after becoming aware of the pregnancy. The Investigator must follow-up and document the course and the

outcome of all pregnancies even if the subject was withdrawn from the clinical study or if the clinical study has finished and if the patient agrees.

All outcomes of pregnancy must be reported by the Investigator to the Sponsor on the pregnancy outcome report form within 2 days after he/she has gained knowledge of the normal delivery or elective abortion.

Any SAE that occurs during pregnancy must be recorded on the Pregnancy Report Form(e.g., maternal serious complications, therapeutic abortion, ectopic pregnancy, stillbirth, neonatal death, congenital anomaly, birth defect) and reported within 24 hours in accordance with the procedure for reporting SAEs.

8.3.2. Clinical Laboratory Assessments

Samples for clinical laboratory assessments will be collected at the time points detailed in the Schedule of Assessments (Table 1). During administration days samples will be collected pre-dose (≤ 1h before IMP administration). Samples will be collected in appropriate tubes and handled according to standard procedures of the applicable laboratory.

Clinical laboratory variables will be determined as outlined in Table 8.

Table 8 Clinical Laboratory Assessments

Hematology	
White blood cell (WBC) count	Neutrophils (percentage and absolute count)
Red blood cell (RBC) count	Lymphocytes (percentage and absolute count)
Hemoglobin (Hb)	Monocytes (percentage and absolute count)
Hematocrit (HCT)	Eosinophils (percentage and absolute count)
Mean corpuscular volume (MCV)	Basophils (percentage and absolute count)
Mean corpuscular hemoglobin (MCH)	Platelet count
Mean corpuscular hemoglobin concentration (MCHC)	RBC distribution width
Coagulation	
Prothrombin time (PT)	International Normalized Ratio (INR)
Activated partial thromboplastin time (aPTT)	
Clinical Chemistry	
Alanine aminotransferase (ALT)	Gamma glutamyl transferase (GGT)
Albumin	Glucose
Alkaline phosphatase (ALP)	Lactate dehydrogenase (LDH)
Aspartate aminotransferase (AST)	Phosphorus
Blood urea nitrogen (BUN)	Potassium
Calcium	Sodium
Chloride	Total bilirubin
Cholesterol	Total protein
Creatinine	Triglycerides
Creatine kinase (CK)	Uric acid
Follicle stimulating hormone (FSH) (Screening Visit onl	y; all female subjects)
Urinalysis	
Bilirubin	Blood
Glucose	pH and specific gravity
Ketones	Protein
Leukocytes	Urobilinogen
Nitrite	
Microscopic (only for abnormal urine stick test findings)	
Viral Serology	
Hepatitis B surface antigen (HBsAg)	Human immunodeficiency virus (HIV)
Hepatitis C virus antibody (anti-HCV)	(Types 1 and 2) antibodies
Urine Drug Screening	
Amphetamines	Cocaine
Barbiturates	Opiates
Benzodiazepines	Phencyclidine (PCP)
Cannabinoids	
Pregnancy Testing	
Serum/urine human beta chorionic gonadotrophin (wom	en of childbearing potential only)

Any value outside the normal range will be flagged for the attention of the Investigator or designee at the site. The Investigator or designee will indicate whether the value is of clinical significance. If the result of any test (or repeat test, if done) from the samples taken during the Screening Period is indicated as clinically significant, the subject will not be allowed to be enrolled into the study without permission of the Medical Monitor and Sponsor. Additional testing during the study may be done if medically indicated. If a clinically significant abnormality in laboratory tests is found during the course of treatment period study, and/or at the final Follow-up Visit, it should be recorded as an AE and the subject will be followed until the test(s) has (have) normalized or stabilized, at the discretion of the Investigator.

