- 12. The patient has any existing or previous history of cancer that has been in remission for less than 5 years prior to Screening.
 - Note: this criterion does not include those participants with basal cell, stage I squamous cell skin cancer or in situ cervical cancer.
- 13. The patient has newly diagnosed diabetes or requires insulin for their treatment; diabetic patients that have had changes to their diabetic treatment regimen within 30 days prior to Screening or diabetic patients that have been hospitalized for their diabetes and/or diabetes related conditions in the past year prior to Screening.
- 14. The patient has long QT syndrome or is under treatment with Class 1A (e.g., quinidine, procainamide) or Class 3 (e.g., amiodarone, sotalol) anti-arrhythmic drugs.
- 15. The patient with acute or chronic hepatitis B or C infection (positive test for hepatitis B surface antigen; positive hepatitis C antibody), known human immunodeficiency virus (HIV) infection, or other acute or ongoing clinically significant viral or bacterial infections..
- 16. The patient has received any depot preparation (sustained-release formulation) of antipsychotic drugs within 1 month (30 days) prior to Screening.

- 17. The patient is considered to be treatment resistant. Treatment resistance is defined as prior non-response to 2 courses of treatment with anti-psychotics of different chemical classes for at least 4 weeks each at doses considered to be effective.
- 18. The patient has received monoamine oxidase (MAO) inhibitors or fluoxetine within 1 month (30 days) before Screening.
- 19. The patient has received electroconvulsive therapy within 6 months (180 days) before Screening.
- 20. The patient has 1 or more laboratory values outside the normal range that are considered by the Investigator to be clinically significant at Screening; or has any of the following at Screening:
 - A serum creatinine value > 1.5 times the upper limit of normal (ULN).
 - A total serum total bilirubin value > 1.5*ULN.
 - A serum alanine aminotransferase (ALT) or aspartate aminotransferase (AST) value > 2*ULN.

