4.1.1. Definitions/derived variables

Unless otherwise specified, baseline is defined as value collected closest but not later than time of the first IMP administration (Day 1). Values for following forms will be used as baseline:

• PANSS on Baseline (Day -1),

- CGI-S on Baseline (Day -1),
- BACS on Baseline (Day -1),
- ESRS on Baseline (Day -1),
- Vital signs pre dose (before IMP administration on Day 1),
- Clinical laboratory data (hematology, biochemistry, urinalysis, coagulation) on Day 1,
- 12-Lead ECG on Baseline (Day -1),
- PK blood sample collection [predose] on Day 1.

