4.1.2. Specifications for summary tables

For **continuous variables**, summary statistics will generally consist of sample size N, number of missing values, arithmetic mean, standard deviation (SD), median, lower and upper quantile, minimum, and maximum. Summaries of PK variables (if data transformation is necessary) will, in addition, contain the geometric mean and the coefficient of variation.

Binary/categorical variables will be summarized and displayed in frequency tables showing sample size, absolute and relative frequencies.

In general, data will be included in summary tables stratified by randomized treatment group.

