4.8.2. Safety laboratory data

Individual data listings of laboratory results will be presented for each subject. Flags will be attached to values outside of the laboratory's reference limits along with the Investigator's assessment. Clinically significant laboratory test abnormalities that were considered AEs by the Investigator will be presented in the AE listings.

Laboratory data will be summarized by type of laboratory test after all results are converted to standard SI units (according to algorithms presented in Data Validation Plan). Descriptive statistics will be calculated for each laboratory parameter at baseline (Day 1) and at each scheduled time point. Shift tables using the categories 'lower than normal range', 'within normal range' and 'higher than normal range' will be provided for each numeric parameter, comparing the baseline value to all post-baseline values. For results expressed as category (in urinalysis) shift tables will present categories: normal and abnormal. Moreover, change from baseline values will also be presented.

Other urinalysis parameters, than those pre-specified in the eCRF, will be listed only.

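### The laboratory shift tables cannot show how large a rise is, and no count by arm above fixed multiples of the upper limit of normal (ULN) is planned

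*Protocol*

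**What the plan says.** The analysis rule is in SAP 4.8.2: "Shift tables using the categories 'lower than normal range', 'within normal range' and 'higher than normal range' will be provided for each numeric parameter". In these tables each patient's class at baseline is set against the class at every later visit. Categorical urinalysis results are split into normal and abnormal. SAP 4.1.1 sets the laboratory baseline: "Clinical laboratory data (hematology, biochemistry, urinalysis, coagulation) on Day 1".

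Exclusion criterion 20 (Protocol 5.3) sets the entry limits. One ground for exclusion at Screening is "A serum alanine aminotransferase (ALT) or aspartate aminotransferase (AST) value > 2*ULN". For bilirubin and creatinine the limit is 1.5 x ULN. Any out-of-range value that the Investigator considers clinically significant at Screening also excludes.

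The shift tables are not the only laboratory output:

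- **Descriptive statistics.** SAP 4.8.2 states: "Descriptive statistics will be calculated for each laboratory parameter at baseline (Day 1) and at each scheduled time point". SAP 4.1.2 includes "median, lower and upper quantile, minimum, and maximum" among the statistics and splits summary tables by arm.
- **Change from baseline and listings.** SAP 4.8.2 plans both. The listings flag out-of-range values and give the Investigator's assessment; SAP 4.1.4 adds the treatment group.
- **AE route.** Protocol 8.3.2 opens with "Any value outside the normal range will be flagged for the attention of the Investigator or designee at the site". It goes on to have the Investigator judge clinical significance and record a clinically significant abnormality found on treatment or at the final follow-up visit as an AE. SAP 4.8.1 counts patients with treatment-emergent AEs by system organ class and preferred term, with further tables by relationship and maximum severity.

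Protocol 10.11.2 promises a categorisation of laboratory results but gives no thresholds. Neither document defines an analysis category by multiples of ULN, a toxicity grade, a combined ALT/AST and bilirubin criterion, or a worst-value count.

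**The concern.** Laboratory results are a named safety endpoint. A three-class table answers whether a value crossed the limit of normal. For liver enzymes, creatinine or creatine kinase (CK), the more useful question is how far above the limit it went, and in how many patients per arm.

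Two losses follow from the stated categories. A patient who starts above range has no higher class to move into, so no rise, however large, registers as a shift. And for a patient who starts within range, a marginal and a marked rise are the same entry. Unless a size-based count is fixed in advance, any later count of marked rises would be post hoc, with cut-points chosen when the treatment groups may already be known.

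**Working it through.** The plan states no figure on this point, so there is nothing to reproduce. The check applies the SAP 4.8.2 rule to illustrative ALT values and then asks what the other outputs recover.

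**1. The three-class rule.** A value above 1 x ULN is classed as high; the lower values used here are classed as within range. All values are illustrative.

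| Baseline (x ULN) | On treatment (x ULN) | Shift-table entry | Above 3 x ULN? |
|---|---|---|---|
| 0.8 | 1.1 | within to high | no |
| 0.8 | 10 | within to high | yes |
| 1.1 | 1.2 | high to high (no shift) | no |
| 1.5 | 8 | high to high (no shift) | yes |
| 2.0 | 2.1 | high to high (no shift) | no |
| 2.0 | 10 | high to high (no shift) | yes |

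The shift table cannot separate rows 1 and 2, nor rows 3 to 6. A count above a fixed multiple separates both sets. The 3 x ULN cut-point is an example and is not in the documents. The baseline values above 1 are all at or below the 2 x ULN that criterion 20 allows at Screening.

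**2. What the other outputs recover.**

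- *Per-visit maximum by arm:* it would show the 1.5 to 8 x ULN case at its visit. It gives one extreme value, not the number of patients past a threshold. It cannot link ALT/AST with bilirubin in the same patient or take each patient's worst value over the treatment period.
- *Change from baseline:* it is in measured units. Conversion to SI units does not align reference limits if laboratories differ.
- *Listings:* they hold every value with arm, but no count.
- *AEs:* they are counted by arm, but entry depends on judgement with no numeric threshold. Protocol 8.3.1.3.1 grades severity by symptoms and effect on daily activities, so an asymptomatic 10 x ULN rise could be graded mild. The severity table therefore does not carry enzyme magnitude.

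**3. How many patients might start above range.** The documents give no figure. If 10-20% do (assumption): 0.10 x 55 = 5.5 and 0.20 x 55 = 11, or about 6 to 11 per arm who cannot show an upward shift.

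**4. What an added count could report (illustration).**

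- 3/55 on one dose versus 0/55 on placebo, by Agresti-Caffo (one success and one failure added per arm): 4/57 - 1/57 = 0.0526. SE = sqrt[(4/57)(53/57)/57 + (1/57)(56/57)/57] = 0.038. 95% CI = 0.0526 ± 1.96 x 0.038, i.e. -2.2 to 12.7 percentage points.
- 0 of 110 active patients: one-sided 95% upper bound = 1 - 0.05^(1/110) = 2.7%.

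**The case against.** The strongest reply is that marked rises are already covered. A reader might infer from the three-class table that they are never counted by arm, or that the trial cannot say how many patients had one. The documents do not support either reading. Rises judged clinically significant become AEs and are counted by arm, maxima and changes from baseline are reported by arm, and every value is listed with its treatment group. What is missing is a prespecified, threshold-based summary, not the data.

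Other parts of the reply also stand:

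- Criterion 20 excludes out-of-range values judged clinically significant at Screening, subject to Medical Monitor and Sponsor permission under Protocol 8.3.2. This narrows the group starting high, and its size is unknown.
- The SAP does deliver what Protocol 10.11.2 promises, so there is no contradiction between the documents.
- No visible text names a hepatic, renal or CK risk for this compound. The toxicology section cannot be read in the public version, so the point is a general one.
- The site-flagging sentence in Protocol 8.3.2 is an operational rule with nothing wrong in it.
- Use of several laboratories is inferred from samples being "handled according to standard procedures of the applicable laboratory" and from the planned unit conversion. It is not stated.

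What the reply does not answer is the loss of magnitude. The AE route depends on judgement and a symptom-based severity scale, and a per-visit maximum neither counts patients nor joins two analytes in one patient. The single cell for rises from normal affects patients who start within range, so the point does not rest on how many start high.

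**Conclusion.** The concern holds in a limited form. The only laboratory categories for numeric parameters are low, within and high, so the shift tables cannot show the size of a rise. No count by arm above fixed multiples of ULN, or of ALT/AST and bilirubin raised together, is planned. Marked rises are counted by arm only through Investigator-reported AEs.

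This is an inexpensive improvement to safety reporting. It is not an error that invalidates the plan, and it does not change sample size, power or significance level. The categorisation result needs only the SAP rule and the entry limits. The 6-11 of 55 per arm rests on an assumed 10-20% above range at baseline. The argument for multiples of ULN as the comparable scale is stronger if several laboratories are used, which is also an assumption.

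**What to change.** In SAP 4.8.2 keep the shift tables and add one table for the Safety Set by treatment received. It gives the number and percentage of patients whose worst post-baseline value exceeds multiples of ULN fixed before unblinding. Examples, for the sponsor to confirm or replace:

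- ALT or AST above 3, 5 and 8 x ULN;
- bilirubin above 2 x ULN;
- ALT or AST above 3 x ULN together with bilirubin above 2 x ULN in the same patient;
- sponsor-chosen multiples for creatinine and CK.

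Report the on-treatment period separately from follow-up, when antipsychotics may have been resumed. Give each difference from placebo with the Agresti-Caffo interval that SAP 4.8.1 already specifies for AEs.

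The cost is a paragraph of SAP text and one table. The values are already collected and the reference limits are already needed for flagging. The drawback is small counts with wide intervals, as the -2.2 to 12.7 point example shows, so the table should be read as descriptive. It concerns reporting only and sets no rule for managing patients.

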8.3.3. Alcohol test

An estimation of blood alcohol content from a breath sample or from an urine sample is to be performed to determine if subject is not under influence of alcohol.

8.3.4. Vital Signs

Vital signs will be assessed at the time points detailed in the Schedule of Assessments (Table 1) and as detailed below:

Respiratory rate (breaths per minute), body temperature (°C), 3-positional blood pressure (systolic and diastolic [mmHg]) and pulse (beats per minute [bpm]) (after 3 minutes lying down; after 3 minute sitting, immediately upon standing; and after 3 minutes standing) will be taken taken once at Screening (Day -10 to -2); once at Baseline (Day -1); thrice on Day 1, Days 2-6 (each day), Day 7, 14, 21 and 28: pre-dose (≤ 1h before IMP administration) and within 5 minutes before or after 1h 45 minutes and 9h post-dose; once during the follow-up visits .

8.3.5. Standard 12-lead Electrocardiograms

Standard safety 12-lead ECGs will be performed at the time points detailed in the Schedule of Assessments (Table 1) and as detailed below. The ECGs will be performed once, pre-dose (\leq 1h before IMP administration) at all scheduled visits when IMP is administered.

- Once at Screening (Days -10 to -2) and at Baseline (Day -1),
- On Days 7, 14, 21 and 28: pre-dose,
- On Follow-up Visits (Days 35 to 42).

The 12-lead ECGs will be performed after the subject has been resting supine for ≥ 5 minutes. The ECG will include all 12 standard leads and a Lead II rhythm strip on the bottom of the tracing. The ECG will be recorded at a paper speed of 25 mm/sec. The following ECG parameters will be collected: PR interval, QRS interval, RR interval, QT interval and QTc interval (QT interval corrected for heart rate using QTcF).

All ECGs must be evaluated by a qualified designee for the presence of abnormalities.

8.3.6. Physical Examinations

Physical examinations will be performed at the time points detailed in the Schedule of Assessments (Table 1) and as detailed below:

- at Screening (Days -10 to -2) and at Baseline (Day -1),
- On Day 28; not earlier than 5h post-dose,
- On Follow-up Visits (Days 35 to 42).

An assessment of general appearance and a review of systems (dermatologic, head, eyes, ears, nose, mouth/throat/neck, thyroid, lymph nodes, respiratory, cardiovascular, gastrointestinal, extremities, musculoskeletal, neurologic and psychiatric systems) will be performed.

8.3.7. Extrapyramidal Side Effects

Extrapyramidal side effects monitoring will be performed at the time points detailed in the Schedule of Assessments (Table 1) and as detailed below:

Extrapyramidal side effects will be monitored starting from Screening, Baseline, and on Day 1, Day 7, Day 14, Day 21, Day 28 and follow-up visits, using the Extrapyramidal Symptom Rating Scale (ESRS). ESRS was developed to assess four types of drug-induced movement disorders (DIMD): Parkinsonism, akathisia, dystonia, and tardive dyskinesia.

ESRS to be conducted during IMP administration days, when start of ratings is to be within 5 minutes before or after 2h post-dose (it will be performed after PANSS, CGI-S, CGI-I and BACS).

8.3.8. Columbia Suicide Severity Rating Scale

Columbia Suicide Severity Rating Scale is a suicidal ideation rating scale created by researchers at Columbia University to evaluate suicide risk. Questions are phrased for use in an interview format, but the C-SSRS may be completed as a self-report measure if necessary. The scale contains

6 "yes" or "not" questions. An individual exhibiting even a single behaviour identified by the scale was 8 to 10 times more likely to commit suicide.

CSSRS will be performed at the time points detailed in the Schedule of Assessments (Table 1) and as detailed below:

Columbia Suicide Severity Rating Scale will be conducted starting from Screening, baseline, on Day 14 and Day 28, and during the follow-up visits,. The C-SSRS should be done AFTER all efficacy and safety assessments/scales.

8.3.9. Additional Safety Variables

Basic neurological, ophthalmological and dermatological assessment will be performed by Investigator. In case of a need, consultation with specialist may be considered and it remains at the Investigator's discretion.

Neurological, ophthalmological, and dermatological examinations will be performed at the time points detailed in the Schedule of Assessments (Table 1) and as detailed below:

Neurological examinations:

- At Screening (Days -10 to -2) and at Baseline (Day -1),
- On Days 7, 14, 21 and 28; not earlier than 5h post-dose,
- On Follow-up Visits (Days 35 to 42).

Ophthalmological examinations:

- At Screening (Days -10 to -2) and at Baseline (Day -1),
- On Day 28 not earlier than 5h post-dose.

Dermatological examinations:

- At Screening (Days -10 to -2) and at Baseline (Day -1),
- On Day 28; not earlier than 5h post-dose.

8.4. Pharmacokinetics Variables

8.4.1. Blood Sample Collection

Blood for the analysis of CPL500036 will be collected at the time points detailed in the Schedule of Assessments (Table 1) and as detailed below.

Blood samples for PK analysis will be collected at the following time-points for extensive PK sampling (approximately 30% of patients):

- Day 1 and Day 7 (steady-state): pre-dose and 0.5, 1, 1.5, 2, 4, 8, 12, and 24* hours post-dose,
- Days 2 to 6: pre-dose* and around 2 hours post-dose,
- Day 28: pre-dose and around 2 hours post-dose.

*please note – the sample 24 hours post-dose on Day 1 it is the same sample as pre-dose on Day 2.

Blood samples for PK analysis will be collected at the following time-points for sparse PK sampling (approximately 70% of the patients):

- Day 1 and Day 7 (steady state): pre-dose and 1, 2, 4 and 8 hours post-dose,
- Day 28: pre-dose and around 2 hours post-dose.

Blood samples are to be collected according to the presented schedule, with the allowable deviation of \pm 1 minute for the first 2 h, \pm 2 minutes for 4-12 h and \pm 30 minute for 24 h post-dose.

Blood samples are to be collected, centrifuged, processed and stored for analysis in accordance with bioanalytical laboratory specified procedure, which is to be provided before the start of the study.

